**Table 3. Primary and Secondary Outcomes**

Domain	Outcome	Data Source	Title	# Items	Timepoints	Description
Primary outcome: Clinical measure	Opioid dose	PCORnet STAR CRN warehouse data derived from electronic health records	n/a	n/a	Baseline and months 6, 12, and 18	Average daily opioid dose in milligrams of morphine equivalent (MED).
Key secondary outcomes: Patient Reported Outcomes (PROs)	Pain interference	Patient survey	PROMIS Short Form v1.0 – Pain Interference 8a	8	Baseline and months 6 and 12	Assesses self-reported consequences of pain on relevant aspects of one's life. 5-point Likert scale. 
	Physical function	Patient survey	PROMIS Short Form v1.0-- Physical Function 8a	8	Baseline and months 6 and 12	Assesses self-reported capability rather than actual performance of physical activities. 5-point Likert scale. 

Note: MED = morphine equivalent dose; PROMIS = Patient-Reported Outcomes Measurement Information System

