#### *PROMIS Pain Interference and Physical Functioning*

Secondary analyses will generate point and interval estimates of mean change in physical function as measured by the 8-item PROMIS-PF scale and mean change in pain interference as measured by the 8-item PROMIS-PI score from baseline to 6 and 12 months and point and interval estimates of the mean difference between the 2 intervention arms. These secondary analyses will use appropriate linear mixed model-based approaches analogous to those described for the primary outcome analysis.

Other secondary outcomes (PROMIS anxiety, PROMIS depression, and BPI pain intensity and pain interference will be analyzed similarly.

We will explore the percentage of participants per group who experienced an increase in pain and a decrease in dose. Additional analyses will compare the treatment groups for the incremental impact of opioid dose -reduction per unit change in pain interference and physical functioning score.

Incidence of self-reported intent to taper opioid medication, collected at baseline, 6 and 12 months, will be compared between treatment groups using chi-square test and logistic regression with adjustment for baseline dose and intent.

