Change in PROMIS pain interference from baseline to 6- and 12-months post-randomization	Continuous	
Pain interference is a measure of the extent to which pain interferes with patient physical, mental, and social activities. It is an outcome that has been identified by patients in the target population as a critical patient-centered outcome for evaluating the potential effects on an opioid-reduction strategy. Pain interference will be measured using a standardized instrument, the 8-item PROMIS-PI scale. The PROMIS-PI scale is a T-score based on PROMIS normative data; a score of 50 represents the average score for the normative population and 10 is the standard deviation (SD) of that population. A higher T-score indicates higher pain interference and worse health.
 
The T score is calculated via online scoring provided by PROMIS (https://www.assessmentcenter.net/ac_scoringservice/templates/UserManual.pdf)
 
The PROMIS Pain Interference scoring manual is found at the below link: https://staging.healthmeasures.net/images/PROMIS/manuals/PROMIS_Pain_Interference_Scoring_Manual.pdf

Change in PROMIS physical functioning from baseline to 6- and 12-months post-randomization	Continuous	
Physical functioning measures one's upper extremities (dexterity), lower extremities (walking and mobility), central regions (back and neck), and instrumental activities of daily living. We will measure physical functioning using the 8-item PROMIS-PF instrument. The PROMIS-PF scale is a T-score based on PROMIS normative data; a score of 50 represents the average score for the normative population and 10 is the standard deviation (SD) of that population. A higher T-score indicates higher physical functioning and better health.
 
The T score is calculated via online scoring provided by PROMIS (https://www.assessmentcenter.net/ac_scoringservice/templates/UserManual.pdf)
 
The PROMIS Physical functioning scoring manual is found at: https://staging.healthmeasures.net/images/PROMIS/manuals/Scoring_Manual_Only/PROMIS_Physical_Function_Scoring_Manual_26May2022.pdf

Other Outcomes		
Change in PROMIS pain intensity from baseline to 6-	Continuous	We will measure pain intensity using the 3-item PROMIS instrument. The PROMIS scale is a T-score based on PROMIS normative data; a score of 50 represents the average score for the

Variable	Type	Definition

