Change in Brief Pain Inventory (BPI) pain severity summary measure from baseline to 6- and 12-months post-randomization.	Continuous	
The BPI assess pain at its “worst”, “least”, “average”, and “now”. Although clinical trials often use pain at “worst” and “average” to represent single pain severity, the BPI’s developers recommend that all four severity items be used, because the models for validation of the BPI included all four items.
 
A composite pain severity score is derived by taking a mean severity score of the four severity questions, if all four items are answered.
 
The BPI severity score is also used to define the participant’s baseline pain severity.
 
The BPI User Guide is found at: https://www.mdanderson.org/documents/Departments-and-Divisions/Symptom-Research/BPI_UserGuide.pdf

BPI pain severity categories	Categorical	
BPI pain severity sub score categories at baseline are defined as (Boonstra 2014):
 
Mild: < 3.5
 
Moderate: 3.5 – 7.4
 
Severe: 7.5+

Change in Brief Pain Inventory (BPI) pain interference summary measure from baseline to 6- and 12-months post-randomization.	Continuous	
The BPI measures how much pain has interfered with seven daily activities: general activity, walking, work, mood, enjoyment of life, relation with others, and sleep. BPI pain interference is scored as the mean of the seven pain interference items, This mean can be derived if more than 50% (or 4 of 7) of the total items have been completed.
 
The BPI User Guide is found at: https://www.mdanderson.org/documents/Departments-and-Divisions/Symptom-Research/BPI_UserGuide.pdf

Variable	Type	Definition
Discontinuation of opioid medications (from T3 Survey) self-report	Binary	
Discontinuation of opioid medication at 12-months will be defined as a response of "No" to the G20 question on the T3 survey that asks: "Are you currently taking an opioid medicine now? Commonly prescribed opioids include hydrocodone, oxycodone, codeine, morphine, and fentanyl." If a participant responds "No" to the survey but has opioid prescriptions in the EHR within 15-days prior to the 12-month timepoint throughout the 18-month timepoint, the participant will be considered as still taking opioid prescriptions.
 
A response of "don't know" will be lumped with a response of yes, both indicate the patient has not discontinued their opioid.

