9.6.5 Exploratory Evaluation of Heterogeneity of Intervention Response to Opioid Use

We will explore treatment heterogeneity for a set of 10 potential covariates listed below, as specified in the protocol and defined in section 9.2 above:

- presence of substance use disorders (yes/no)
- presence of comorbid diseases (Charlson comorbidity index none vs 1 or more),
- Age (< 50, 50-64, 65+),
- baseline pain (BPI pain severity score of mild, moderate, severe),

- health literacy (high, average, and low),
- BMI categories (obese vs. not obese),
- Taking non-opioid pain medications prescribed (yes/no) per T1 survey
- Baseline opioid dose categories (very low, low, moderate, and high).
- Intervention delivery mode (in-person vs. telehealth),
- Number of intervention visits/sessions received: 0, 1-2, 3-4, >4

Testing for heterogeneity of intervention effects for these subgroups will be considered *exploratory*, and the results will be interpreted with appropriate caution. The outcome of interest for these analyses will be change from baseline to 12-months in average prescribed daily opioid dose (in MED). Analyses for these 10 covariates will be conducted the same as for the 2 specified subgroups above (Section 9.6.4), except that p-values will be interpreted descriptively only.

Each covariate will be added individually to a repeated measures MMRM models similar to the primary model described above while intervention arm is still adjusted for in the model .

9.6.6 Percent of Participants Who Experienced an Increase in Pain and Decrease in Opioid Dose

We will explore the percentage of participants per intervention arm who experienced an increase in pain and a decrease in opioid dose. For this analysis, we will create a binary variable for both the PROMIS Pain Interference and Physical Functioning outcomes that identifies participants that experienced an increase in these measures at 12-months since baseline (i.e.: an increase in the Pain Interference T-Score at 12-months and a decrease in the Physical Functioning T-Score at 12-months). We will then categorize their opioid use at 12-months in comparison to baseline as: unchanged (within +/- 10 MED), decreased (<10 MED), or increased (>10 MED).

We will provide descriptive statistics via contingency table that displays the count and proportion of participants, per intervention arm, that experienced an increase in pain but a decrease in opioid prescriptions. No hypothesis or statistical testing will occur.

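### SAP 9.6.6 labels as 'increase in pain' a flag built only from pain interference and physical function, so its pain-up/dose-down table holds no measure of pain intensity

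*SAP*

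**What the plan says.** Protocol 5.3.2 introduces the analysis in one sentence: "We will explore the percentage of participants per group who experienced an increase in pain and a decrease in dose". It names no instrument. The sentence stands under a subsection headed with the two PROMIS key secondary scales.

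SAP 9.6.6 takes it up: "We will explore the percentage of participants per intervention arm who experienced an increase in pain and a decrease in opioid dose". It then defines the pain side through those two scales alone: "we will create a binary variable for both the PROMIS Pain Interference and Physical Functioning outcomes that identifies participants", with the direction given as "an increase in the Pain Interference T-Score at 12-months and a decrease in the Physical Functioning T-Score at 12-months". The output is a contingency table by arm of those "that experienced an increase in pain but a decrease in opioid prescriptions. No hypothesis or statistical testing will occur".

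Two scales for the level of pain are also in the plan. For PROMIS Pain Intensity 3a, SAP 9.2 says "We will measure pain intensity using the 3-item PROMIS instrument". For the BPI, SAP 9.2 says "A composite pain severity score is derived by taking a mean severity score of the four severity questions", provided that all four are answered. Protocol Table 4 schedules both at baseline, 6 and 12 months.

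**The concern.** The table's label and its content do not match. A reader who meets a row for increased pain with decreased dose will expect it to say how often pain went up. As defined, it says how often interference rose and physical function fell. The function part is not specific to pain, since function can decline for many other reasons.

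The question matters because Protocol 8.1.5 names increased pain as a possible consequence of reducing or stopping opioids. Increased pain is not among the reportable events in Protocol Table 11 and is not an event term in SAP 9.7. SAP 9.6.6 is the one planned analysis that pairs worsening in the individual participant with a fall in that participant's dose.

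**Working it through.** The plan gives no figure to reproduce here. The check compares definitions and then adds a small illustration.

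**1. What each scale measures, in the documents' own terms**
- Pain interference (Protocol Table 3): "Assesses self-reported consequences of pain on relevant aspects of one's life".
- Physical function (Protocol Table 3): self-reported capability, with no reference to pain.
- PROMIS Pain Intensity 3a (Protocol Table 4): how much the person hurts.
- BPI intensity items (Protocol Table 4): level of pain over the past week, scored 0 to 10.

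Only the last two measure pain level, and neither enters SAP 9.6.6.

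**2. How the SAP uses the word elsewhere.** SAP 9.6.5, immediately before, defines baseline pain by BPI pain severity. The meaning of 'pain' therefore changes between two consecutive sections.

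**3. Whether intensity is crossed with dose anywhere else.** SAP 9.6.1 compares mean change in both intensity scores between arms. It does not cross them with dose change, and no other SAP section does.

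**4. Whether the scales can part company.** In the small randomized taper-support trial described in Protocol 1.3 (N = 35), pain severity did not differ significantly between groups (difference -0.68, 95% CI -2.01 to 0.64), while interference improved significantly more with support. One significant and one non-significant result do not prove that the scales diverge, but they show that the two should be reported separately.

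**5. Illustration of disagreement.** Assume 12-month changes in intensity and in the proxy are bivariate normal with mean 0 and correlation r. The documents give no value for r.

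P(opposite directions) = 1/2 − arcsin(r)/π
- r = 0.3: 0.5 − 0.3047/3.1416 = 0.403
- r = 0.5: 0.5 − 0.5236/3.1416 = 0.333
- r = 0.7: 0.5 − 0.7754/3.1416 = 0.253
- r = 0.8: 0.5 − 0.9273/3.1416 = 0.205

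Under this model the same fractions apply among participants whose intensity rose. At r = 0.3 to 0.7, 40% to 25% of them would not be flagged by the proxy.

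**6. What this does to the arm percentages.** Under the same model both scales flag 50% of participants, so the errors cancel in the margin. The pain-up/dose-down percentage would move only if the scales relate differently to dose change or if their mean changes differ. As an example of the second case, take the SAP section 6 values for interference (SD of change 10, minimally important difference 3.5). A mean improvement of 3.5 in one arm would leave Φ(−3.5/10) = 36% flagged as worse, against 50% on an intensity scale with no mean change. Nothing in the documents says that this will happen.

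**7. Separate or joint flags.** SAP 9.6.6 speaks of a binary variable for both outcomes and joins the two directions with 'and'. With zero mean changes, each flag alone marks 50%. A joint flag marks 1/4 + arcsin(r)/(2π), where r is now the assumed correlation between worsening on the two scales: 30%, 33% and 37% at r = 0.3, 0.5 and 0.7. The two readings give clearly different tables.

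**The case against.** The strongest reply is that the SAP's choice is reasonable and open. Protocol 4.1.2 calls PROMIS Pain Interference a standard outcome in pain trials. It is a key secondary endpoint, and SAP 9.2 presents it as critical to patients when judging an opioid-reduction strategy. The protocol sentence stands under the interference and function heading and names no instrument. The operational definition is written in the same SAP paragraph as the label. The table shells are in a separate file that may carry clearer titles. Intensity is compared between arms in SAP 9.6.1.

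Most of this stands. A reader might infer that the table contains no measure of pain at all; that is too strong, because interference is pain-specific. A reader might also infer that the SAP departs from the protocol. The documents do not support that either, because the protocol leaves the instrument open. The heading does not settle the matter the other way: the same subsection also covers anxiety, depression, the BPI scales and intent to taper. Nor can it be said that a decline in function alone counts as increased pain, since under a joint flag it would not.

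The reply leaves one thing unanswered. An arm comparison of mean intensity does not show whether the participants whose dose fell are those whose pain rose.

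**Conclusion.** The point holds as a limit on one descriptive table. Followed as written, SAP 9.6.6 yields a display labelled as pain that contains no measure of pain intensity and has a non-specific function decline in its definition. It also leaves the combination of the two flags unspecified. The primary and key secondary inferences are unaffected.

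The size cannot be computed from the documents. The 25% to 40% disagreement rests on an assumed correlation, zero mean changes and normality, and it falls to about 20% at r = 0.8. A reader might take it as the error in the reported arm percentages. It is not: it concerns the classification of individuals, and no bias in the percentages or between arms has been shown. The finding itself rests on the definitions in steps 1 to 3, which need no assumption.

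**What to change.** In SAP 9.6.6:
- Add an 'increase in pain' flag based on change from baseline to 12 months in one named intensity score, for example PROMIS Pain Intensity 3a, crossed with the existing dose-change categories by arm. Write the name in full, because SAP 3.2 uses the abbreviation PROMIS-PI for both the interference and the intensity form.
- Show BPI pain severity as a supportive display, noting that it needs all four items and so may lose further cases when survey completion is already about 60% (SAP section 6).
- Tabulate the two existing flags separately, labelled 'worse pain interference' and 'worse physical function'.

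Name the main intensity score before arm-level results are seen, so that the choice is not left to the analyst. The cost is a few lines of SAP text and one extra descriptive display (two with the BPI version). The scores are already collected and derived, and SAP section 11 allows displays to be added without an amendment if they do not contradict the SAP text. If no display is added, relabelling the existing flags is the minimum.

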The data available from Liebschutz and Sullivan et al. indicate opioid doses are approximately normally distributed on the natural log (ln) scale. If the change from baseline in opioid dose is also lognormally distributed, then based on the assumptions above the standard deviation of the change from baseline ln-dose, after adjusting for baseline dose would be approximately 0.650. Correspondingly, 253 participants per study arm provides 80% power to identify a 15% relative dose reduction.

To account for potential variance inflation associated with CBT group delivery (based on a group size of 8 and an interclass correlation coefficient of 0.01) and a potential loss of follow-up information on as many as 10% to 12% of participants because of attrition, the sample size was inflated by 20% to yield a total randomized size of 304 per study arm needed for the primary outcome at 12 months. Therefore, the total study sample size will be 608 randomized participants (**Table 7**).

Additional estimates of sample size requirements were generated based on the known psychometric properties of the secondary outcomes, PROMIS physical functioning and pain interference, under the assumption that at least 80% power is desired for the PROMIS Pain Interference scales. The scoring algorithm for the PROMIS scales is designed to construct a 100-point scale with a mean of 50 and standard deviation of 10. Furthermore, studies of the properties of the instruments indicate that the minimally important difference (MID) for the physical function scale is 2 units, whereas the MID for the pain interference scale is 3.5 units. Under an assumption of independent observations, a sample size of 786 evaluable participants would be required to achieve 80% power to detect the MID of 2.0 units for the physical function scale, and a sample size of 260 evaluable participants would be required to achieve 80% power to detect the MID of 3.5 units for the pain interference scale. With the planned total of 608 randomized participants, the power for the PROMIS Pain Interference score is 96%, while the power for the PROMIS Physical Functioning scale is 57%, with a 25% increase to account for attrition or missing PROMIS scale responses. No power calculations have been specified for subgroup assessments (**Table 8**).

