6. SAMPLE SIZE DETERMINATION

Sample size estimates were generated to provide robust power to detect minimal clinically important differences (MCID) in reduction of opioid use between the 2 study arms.

A total sample size of 506 participants (253 per study arm) will provide 80% power to detect an effect size of a difference of 10 MED between the SDM and MI+CBT intervention arm using an analysis of covariance model with $\alpha=0.05$ and assuming a baseline model-adjusted standard deviation for change from baseline of 40 MED. The sample size was inflated by 20% (608 total participants; 304 per study arm) to account for potential variance inflation associated with CBT group delivery (based on a group

size of 8 and an interclass correlation coefficient of 0.01) and a potential loss of follow-up opioid prescription data on as many as 12% of participants.

For the PROMIS secondary outcome measures, the minimally important difference (MID) for the physical function scale is 2 units, whereas the MID for the pain interference scale is 3.5 units. For both instruments, we assume the standard deviation for change from baseline is 10 (see section 9.2 for a more thorough description of these secondary measures). With the planned total of 608 randomized participants and assuming 20% of those have missing PROMIS scale responses, the power for the PROMIS Pain Interference score is 96%, while the power for the PROMIS Physical Functioning scale is 57% (Table 6.1).

Note that the enrollment was slower than planned, and due to timeline constraints was stopped prior to reaching 608 randomized participants. Final study enrollment was 526 randomized participants. As of June 2023 (DSMB report), study discontinuation was at 20%;, but survey completion rate was tracking around 60% (40% missing, higher than the planned levels). Approximate post-hoc power based on the final sample size is provided in Table 6.1.

Table 6.1. Power for Primary and Key Secondary Outcomes

Total sample size	Primary aim: Power for opioid MED ¹	Secondary aim: power for PROMIS Pain Interference ²	Secondary aim: Power for PROMIS Physical Functioning ²
Planned 608	80%	96%	57%
Approximate post hoc power based on randomized (n=526)	75% based on protocol- assumed level of missing opioid prescription data	85% Based on number of completed surveys	40% Based on number of completed surveys

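### The dose-change categories in SAP 9.6.6 overlap as written: the decreased category takes in unchanged participants and rises below 10 MED

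*SAP*

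**What the plan says.** Protocol 5.3.2 is the source of the analysis: "We will explore the percentage of participants per group who experienced an increase in pain and a decrease in dose". It sets no threshold for pain or for dose.

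SAP 9.6.6 turns this into rules.

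- **Pain and function:** "we will create a binary variable for both the PROMIS Pain Interference and Physical Functioning outcomes". Worsening is defined by direction only, as "an increase in the Pain Interference T-Score at 12-months and a decrease in the Physical Functioning T-Score at 12-months".
- **Dose:** 12-month dose against baseline is classed as "unchanged (within +/- 10 MED), decreased (<10 MED), or increased (>10 MED").
- **Status:** a contingency table by arm. "No hypothesis or statistical testing will occur".

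Elsewhere the SAP uses 10 MED differently. Sections 3.1.3 and 9.4 treat a fall of 10 MED as the clinically significant change. Section 9.2 creates an indicator for a change from baseline of at least 10 MED, so exactly 10 counts.

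For the PROMIS scales, Protocol 5.4 and SAP 6 state that "the minimally important difference (MID) for the physical function scale is 2 units, whereas the MID for the pain interference scale is 3.5 units". SAP 9.6.6 does not use these values.

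**The concern.** The three dose categories should be exclusive and exhaustive. As printed, the decreased category has no minus sign. It therefore contains the whole unchanged band except exactly +10, together with rises of up to just under 10 MED. If programmed as written, the table double-counts participants, and the cell it exists to report (pain up, dose down) takes in people whose dose did not meaningfully fall.

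Two smaller points affect the same table. The text does not say whether pain interference and physical function give two flags or one combined flag. And the dose axis has a tolerance band while the PROMIS axes have none, so the smallest adverse movement in T-score counts as worsening.

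At stake is the reading of one exploratory display. It is, however, the only place in the SAP that joins dose reduction and worsening in the same participant. No comparison accompanies it, so the raw percentage is all a reader will see.

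**Working it through.** SAP 9.6.6 states no numerical result, so there is no figure of its own to reproduce. As a check on the shared inputs, the sample sizes in Protocol Table 7 were recomputed with n per arm = 2 × (1.96 + 0.84)² × (SD/difference)²:

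- MED, 10 with SD 40: 252 per arm, 504 in total (stated 506)
- pain interference, 3.5 with SD 10: 258 in total (stated 260)
- physical function, 2 with SD 10: 786 in total (stated 786)

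The inputs are being read as the plan intends.

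**Inputs**

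- SD of dose change: SAP 6 is "assuming a baseline model-adjusted standard deviation for change from baseline of 40 MED". The table sorts unadjusted change. Protocol 5.4 gives a dose-level SD of 80 MED and expects the SD of change to be of similar size, so 80 is shown as well. SD 20 is an assumption, added for range.
- SD of PROMIS change: SAP 6 says "we assume the standard deviation for change from baseline is 10". SD 5 and SD 3 below are assumptions.
- Mean change 0, normal distribution, and independence of pain and dose change: assumptions.

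**Dose categories.** With Φ the standard normal distribution function:

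- true fall (below -10) = Φ(-10/SD)
- unchanged = Φ(10/SD) - Φ(-10/SD)
- decreased as written (below +10) = Φ(10/SD)
- increased = 1 - Φ(10/SD)

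The last two columns multiply the decreased share by a 50% pain flag.

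| SD | Below -10 | Unchanged | Decreased as written | Increased | Literal total | Cell, below -10 | Cell, as written |
|---|---|---|---|---|---|---|---|
| 20 | 30.9% | 38.3% | 69.1% | 30.9% | 138% | 15.4% | 34.6% |
| 40 | 40.1% | 19.7% | 59.9% | 40.1% | 120% | 20.1% | 29.9% |
| 80 | 45.0% | 9.9% | 55.0% | 45.0% | 110% | 22.5% | 27.5% |

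At SD 40, about 20% of participants fall in two categories and the key cell grows by about half (29.9/20.1 = 1.49). With the minus sign restored, the categories are about 40%, 20% and 40%, and sum to 100%.

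**Boundary.** For exactly -10 or +10 MED, SAP 9.6.6 gives unchanged (within the band), while the SAP 9.2 indicator is met.

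**PROMIS flags.** With no true change and symmetric error, P(change > 0) = 50% for each measure, whatever the SD. This is an upper value:

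- Ties (assumed score steps of 1 to 2 points) lower it to 46–48% at SD 10 and 37–43% at SD 3.
- If one combined flag needs both measures to worsen, the share is 1/4 + arcsin(r)/(2π), which is 25%, 33% and 43% for assumed correlations r of 0, 0.5 and 0.9.

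With the stated minimally important differences as cut-offs:

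- pain interference, rise of at least 3.5: 1 - Φ(3.5/10) = 36% at SD 10, and 24% at SD 5
- physical function, fall of at least 2: 1 - Φ(2/10) = 42% at SD 10, and about 34% at SD 5

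**The case against.** The strongest reply is that this is a missing minus sign. The other two categories leave only falls of more than 10 MED for the third, the section title speaks of a decrease in dose, and SAP 3.1.3 and 9.4 define the relevant change as a fall of 10 MED. A programmer is unlikely to count a rise as a decrease, and the derivation file and table shells, which are separate, may have it right. The intended meaning is indeed fairly clear, which makes this minor. But nothing in either document corrects the rule, and restoring the sign would still leave the clash with SAP 9.2 at exactly 10 MED.

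On the PROMIS side, the reply is that counting any worsening is a defensible, sensitive choice for a descriptive look at harm, and that 3.5 and 2 are not individual cut-offs. This also stands. Protocol Table 7 presents them as mean differences between groups, used for power. At the plan's SD of 10 they still flag 36% and 42% of people with no true change, so they cannot be presented as removing noise. They belong beside the any-change version, not in its place.

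Finally, the same rule applies to both arms, nothing is tested, and no decision rests on the table. That is correct and limits the weight of the point.

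**Conclusion.** The dose rule in SAP 9.6.6 is wrong as written and should be corrected. Followed literally, it double-counts about 20% of participants and raises the pain-up/dose-down cell from about 20% to 30%. Those figures rest on mean change 0, SD 40, normality, independence and a 50% pain flag. At SD 80 the double count is about 10% and the cell goes from 22.5% to 27.5%. The mismatch at exactly 10 MED and the unclear number of PROMIS flags are smaller defects in the same paragraph. The matter is minor.

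Three stronger readings are tempting, and the documents do not support them.

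- **That about half of unchanged participants will appear harmed.** The 50% is the marginal rate of a single PROMIS flag under no true change. The reported cell also needs a fall in dose, and is about 20% under the same assumptions with the sign restored.
- **That the table mainly reports noise and will overstate harm.** The SD of 10 describes all variation in change between people, not measurement error alone, and the documents give no error SD.
- **That this is the plan's only look at whether dose reduction costs pain or function.** Protocol 5.3.2 also plans an incremental-impact analysis relating dose reduction to change in the two scores, although the SAP does not develop it. SAP 9.5.1 and 9.6.1 model PROMIS and BPI changes between arms. What is true is narrower: this is the SAP's only joint look at participant level.

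**What to change.** In SAP 9.6.6, define dose change as 12-month minus baseline average daily MED, with three categories consistent with SAP 9.2:

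- decreased: -10 MED or less
- unchanged: greater than -10 and less than +10 MED
- increased: +10 MED or more

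State that pain-interference worsening and physical-function worsening are separate flags, each tabulated against dose change by arm. Keep the any-change version. Beside it, show one using a rise of at least 3.5 for pain interference and a fall of at least 2 for physical function. Add a note that the plan states these values as between-group differences and that they reduce noise without removing it.

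Check that the derivation file and table shells carry the same categories.

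The cost is one paragraph of SAP wording and one extra panel. No new data, test or sample size is needed. The MID-based panel will class fewer participants as worse, which is why both versions should be shown.
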